6.7.1. Source data verification

Investigation source data are: the CRFs, Informed Consent Forms, Letter of Authority, randomisations envelopes, interview notes, output from uroflowmetry and print.

All data collected can be directly entered in the CRF and in case site write source data in medical records or nurse notes this will be described in the site specific "Source data specification form" (sponsor ref. number VV-0190745). Only the investigator, delegated site personnel and the sponsor representatives (personnel within Medical Affairs/Clinical Operations) will have access to all the CRFs.

6.7.2. Other methods for data quality assurance

The sponsor, sponsor's representative and/or investigational sites may be inspected by competent authorities or their representatives and likewise may be audited per Coloplast internal quality audit plan and procedures.

7. Statistical considerations

7.1. Statistical design, method and analytical procedures

Design

The study is a single blinded, randomised, crossover study divided into two parts; Part A and Part B.

- Part A evaluates 2 prototypes of intermittent catheters compared to a standard SpeediCath® Flex catheter.

Populations

Intention to Treat (ITT) and Safety populations will be defined at a formal data review meeting just before database lock. As a minimum, the clinical manager and the statistician will be involved in the classification of subjects.

The **ITT population** will be constituted by all randomised subjects with valid informed consent who have been exposed to at least one product, and with valid information on at least one product with respect to either primary or secondary endpoints. Any exclusion of subjects from the ITT set beyond this must be separately documented.

The **Safety population** (basis for AE summary) will be constituted by subjects that have given informed consent and have been exposed to at least one product.

A formal PP population is not planned due to the explorative nature of the investigation. Considering the data obtained it might however be considered to make additional explorative analyses based on a subset of the ITT population.

Individual endpoints/data points may be excluded from analysis, even though the corresponding subject belongs to the ITT population. This could for example be due to protocol violations at one test day that would affect the primary endpoint at the corresponding test day, but have no impact on the primary endpoint on the remaining test days. Any exclusion of endpoints/data points will be documented.

General

All efficacy will be based upon the ITT (intention to treat) population and adverse events will be summarized based on the safety population.

If data is represented by a curve (e.g. pressure and force), relevant characteristics of the curve (e.g. peak of the curve) will be summarised and/or listed.

Where meaningful, data will be summarised and/or listed. Additional explorative post-hoc analyses can be performed if deemed relevant.

Primary endpoint

A mixed model, for part A and B respectively, with subject included as a random component will be applied for the primary analysis of the urine flow rate.

Treatment (SpeediCath® Flex, test product 2, test product 3 (part A) and SpeediCath® Flex catheter and Test product 2 (part B) [REDACTED]) and Day of catheterisation visit (1, 2, 3, 5 and 6) will be included as fixed effects with age as a covariate. The contrast between the catheters as well as the 95% confidence intervals will be estimated using Proc Mixed in SAS.

Secondary endpoints

Discomfort, measured on a VAS scale and post void residual urine will be analysed using a linear mixed model, for part A and B respectively, same as described in the primary endpoint

Adverse events will be summarised and/or listed based on the safety population.

Haematuria data will be listed.

The odds ratio between the test products as well as the corresponding 95% confidence intervals will be estimated.

All statistical analyses will be made with SAS version 9.4 (SAS Institute Inc., Cary, NC).

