6.1.1. End points and rationale for selection

End points	Type of assessment	Rationale for selection of end points
Primary end points	Urine flow rate	
Urine flow rate, measured by uroflowmetry, are an indicator for the test product performance.
 
Secondary end points	Post void residual urine	
Post void residual urine, measured with an ultrasound bladder scan are indicator for the test product performance.

	Amount of urine left in bladder (ml)	
Macroscopic haematuria is measured by assessing visible blood during catheterisation. This is an indicator for test product safety.

	
Did you experience visual blood during catheterisation (No/Yes) If yes, where was the blood (several answers accepted) (On the tip – at the eyelets – on the whole catheter – in the urine) 7 answer possibilities
	
Microscopic haematuria will be measured after each catheterisation using urine dipstick. This is an indicator for test product safety.

	
Negative - Neg - Non-hemolysed 10 Ery/µL (+/-) - Hemolysed 10 Ery/µL (+/-)
	
	
Positive - Non-hemolysed 80 Ery/µL (2+) - Hemolysed 25 Ery/µL (1+) - Hemolysed 80 Ery/µL (2+) - Hemolysed 200 Ery/µL (3+)
	
	
At least one positive response makes endpoint considered positive
	
This is an indicator for test product safety.

Explorative end points	Adverse events Overall discomfort during catheterisation	
Discomfort will be measured both during catheterisation, insertion, withdrawal and during post catheterisation

End points	Type of assessment	Rationale for selection of end points

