Discomfort during insertion	
vertical line indicating how you experienced the overall catheterisation.
 
On a scale ranging from "no discomfort" to "worst possible discomfort" caused by the catheter, set a vertical line indicating how you experienced the insertion of the catheter.
 
On a scale ranging from "no discomfort" to "worst possible discomfort" caused by the catheter, set a vertical line indicating how you experienced the withdrawal of the catheter.
 
On a scale ranging from "no discomfort" to "worst possible discomfort" caused by the catheter, set a vertical line indicating how you experienced urination after the catheterisation.
 
How did you experience insertion of the catheter? (5 point scale: Very difficult – difficult – neither difficult nor easy – easy – very easy)
 
How did you experience withdrawal of the catheter? (5 point scale: Very difficult – difficult – neither difficult nor easy – easy – very easy)
 
Did you touch the coated part of the catheter during insertion? (Yes/No)
 
Did you experience urine running out of the catheters on the outside of the catheters? (Yes/No)
	
to investigate potential differences. Discomfort is measured by VAS-scale (10 cm horizontally line) – (assessed by subjects)
 
As the catheter design is relatively new, handling will be investigated and the information utilized in further development.

Discomfort during withdrawal		
Discomfort during urination post catheterisation		
Handling during insertion		
Handling during withdrawal		
Handling during insertion		
Handling during catheterisation		
Urine flow	
 - Micturition time (sec) - Flow time (sec) - Time to Qmax (sec) - Micturition volume (ml) 	
Urine flow, measured by uroflowmetry, are an indicator for the test product performance.
 

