Subject is asked about symptoms for urinary tract infections (frequent urination, stinging or pain at urination) and use of analgetica up to 24 hours prior to the visit. In addition, a urine sample is made and microscopic haematuria, nitrite and leukocytes is measured before catheterisation to further ensure no symptoms of urinary tract infection or damage to the urinary tract system. If negative for these symptoms, use of analgetica and microscopic haematuria/nitrite/leukocytes, the subject will be catheterised with the randomised product and urine flow rate is measured. Hereafter the bladder is scanned for post void residual urine, by using a hand held bladderscanner, [REDACTED]. The subject is offered something to drink and after 1-2 hours a urine sample is made and microscopic haematuria measured. Subject and nurse register relevant answers in CRF, including possible adverse events. In addition, subject register the end points regarding discomfort (VAS-scale) and the nurse register the assessments in the CRF. Next visit is scheduled.

If subjects have agreed to participate in interviews, Test Visit 3 will be prolonged to include interview.

Test Visit (V5-V6) – approximately two hours

Subject is asked about symptoms for urinary tract infections (frequent urination, stinging or pain at urination) and use of analgetica up to 24 hours prior to the visit. In addition, a urine sample is made and microscopic haematuria, nitrite and leukocytes is measured before catheterisation to further ensure no symptoms of urinary

tract infection or damage to the urinary tract system. If negative for these symptoms, use of analgetica and microscopic haematuria/leukocytes/nitrite, the subject will be catheterised with the randomised product [REDACTED] [REDACTED] and urine flow rate is measured. Hereafter the bladder is scanned for post void residual urine, by using a hand held bladderscanner, [REDACTED]. The subject is offered something to drink and after 1-2 hours a urine sample is made and microscopic haematuria measured. Subject and nurse register relevant answers in CRF, including possible adverse events. In addition, subject register the end points regarding discomfort (VAS-scale) and the nurse register the assessments in the CRF. Next visit is scheduled.

If subjects have agreed to participate in interviews, Test Visit 6 will be prolonged to include interview. At the end of Test Visit 6 the termination page in CRF is completed by nurse.

Interview – plus one hour

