Subjects will be asked if they would like to participate in interviews following Test Visit 3 and 6. A Coloplast representative will interview the subjects asking questions related to their experience with the catheter. The subjects will be asked to sign a specific consent form to participate in interview. In addition, subjects will be asked for consent to tape recording and filming during the interviews, but can participate in interviews without this. The investigator and/or study personnel will be interviewed by a Coloplast representative asking questions related to their experience with the catheters.

Urinary tract infection suspicion

If the subject shows symptoms of urinary tract infections he will be referred to his own physician for further examination. When the subject has been examined and treated for eventual urinary tract infections, and shows no symptoms for urinary tract infections, his visits can be rescheduled if possible before LPO. If not possible to complete all visits before LPO, the subjects should complete all possible visits.

Use of analgesics

If the subject used analgesics within 24 hours prior to a visit, this will be documented in the Concomitant Medication Form and the visit will be rescheduled.

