6.4.4. Flow-chart

Table 4 chart showing the connection between visits and assessments.

	PERFORMED BY	SOURCE	INFORMATION AND INCLUSION VISIT 0	VISIT 1-3	VISIT 5-6	TERMINATION VISIT
General						
Oral information	Investigator	NA	X			
Written informed consent	Subject	Informed consent form	X			
Signed Letter of authority	Investigator	Letter of Authority Form	X			
Consent to interview	Subject	Informed consent form - Interview	X			
Check of in- and exclusion criteria	Investigator	CRF	X			
Allocation to subject number	Investigator	CRF	X			
Randomisation	Investigator	Randomisation Envelope	X			
Insurance of subjects well-being and compliance with CIP	Investigator	CRF	X	X	X	X
Registration of Demographic						
Date of birth	Investigator	CRF	X			
Check for symptoms of UTI, damage to urine tract system and use of analgesics before catheterisation						
Urine sample from subject	Subject	NA		X	X	
Leukocytes (urine dipstick)	Investigator	CRF		X	X	
Nitrite (urine dipstick)	Investigator	CRF		X	X	
Haematuria – microscopic (urine dipstick - erythrocytes)	Investigator	CRF		X	X	
Check for use of analgesics 24 hours before catheterisation	Investigator	CRF		X	X	
Catheterisation per randomisation	Investigator	CRF		X	X	
Registration/measurement of primary end points – during catheterisation						
Urine flow rate - Max flow ($\frac{ml}{s}$) - Middle flow ($\frac{ml}{s}$)	Investigator	CRF (or possible printed graph)		X	X	
Registration/measurement of secondary end points - after catheterisation						
Post void residual urine	Investigator	CRF (or possible print)		X	X	
Haematuria – macroscopic (visible blood)	Investigator	CRF		X	X	
Urine sample from subject	Subject	NA		X	X	
Haematuria – microscopic (urine dipstick)	Investigator	CRF		X	X	
AEs/ADEs/SAEs/SADEs	Investigator	CRF		X	X	X
Registration of explorative end points						
Overall discomfort during catheterisation	Subject	CRF		X	X	X
Discomfort during insertion	Subject	CRF		X	X	

Discomfort during withdrawal	Subject	CRF		X	X	
Discomfort during urination post catheterisation	Subject	CRF		X	X	
Handling during insertion	Investigator	CRF		X	X	
Handling during withdrawal	Investigator	CRF		X	X	
Handling during insertion	Investigator	CRF		X	X	
Handling during catheterisation	Investigator	CRF		X	X	
Interview	Coloplast representative	Interview notes		V3	V6	
Urine flow - Micturition time (sec) - Flow time (sec) [REDACTED] - Micturition volume (ml)	Investigator	CRF (or possible printed graph)		X	X	
Registration of termination						

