7.3. Level of significance and power

Statistical tests will be carried out as two sided tests on a 5% level of significance.

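### Should the urine flow-rate model adjust for bladder volume, given that its only covariate is age?

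*Combined protocol and SAP*

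**What the plan says.** Section 7.1 (Primary endpoint) specifies a mixed model for each part, with subject as a random term and treatment as a fixed effect. It adds that "Day of catheterisation visit (1, 2, 3, 5 and 6) will be included as fixed effects with age as a covariate". Discomfort and post void residual use a linear mixed model "for part A and B respectively, same as described in the primary endpoint".

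Other sections that bear on the point:

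- The flow-chart in 6.4.4 records date of birth once, at Visit 0. It marks micturition volume and post void residual at Visits 1-3 and 5-6.
- Section 6.4.1 has the subject give a urine sample, then be catheterised while flow is measured. "Hereafter the bladder is scanned for post void residual urine, by using a hand held bladderscanner". Parts of this text are blacked out; the readable part sets no bladder volume.
- Section 6.1.1 includes the handling question "Did you experience urine running out of the catheters on the outside of the catheters".
- Section 6.4.1 foresees incomplete data after a suspected infection: "If not possible to complete all visits before LPO, the subjects should complete all possible visits".
- Section 7.1 leaves room for further explorative analyses, section 7.2 gives no sample-size calculation, and section 7.5 sets no criterion for success.

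**The concern.** The one named covariate appears to do no work. Age does not vary between a subject's visits, so it cannot explain why his flow differs from one catheter to the next. Bladder volume at catheterisation does vary between visits and could plausibly affect flow. It could be approximated as drained volume plus residual, both already collected.

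Two things would be at stake. One is precision in a ten-subject comparison, where any volume-related variation stays in the residual error. The other is pre-specification: a volume adjustment chosen after the data are seen is weaker evidence than one fixed in 7.1.

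**Working it through.** **Inputs.** Ten subjects (7.2); three products over Test Visits 1-3 in Part A (6.1); "Statistical tests will be carried out as two sided tests on a 5% level of significance" (7.3). The documents give no SD, effect size, power or volume-flow correlation, so there is no stated figure to reproduce. Results are in units of SDw, the within-subject SD of flow. The within-subject volume-flow correlation, rho, is an assumption and is varied.

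**Step 1: does age do harm?** With complete data every subject has all three products and all three visits, so the contrasts are purely within-subject and orthogonal to any subject constant.

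- In 300 simulated trials (REML, random subject), adding age changed the contrasts by at most 6e-14.
- The standard error was unchanged (relative change below 3e-8) whenever the estimated subject variance was above zero. When it was estimated as zero, the contrast still held but the SE ratio ranged from 0.86 to 1.02. This happened in 0 of 150 trials with a between-subject SD of 3 ml/s, and in 78 of 150 with no subject variance beyond age.
- With 3 of 30 values missing and SDw assumed to be 2 ml/s, age moved a contrast by a median of 0.03 to 0.07 ml/s (maximum 0.33 to 0.55). The complete-data half-width from Step 2 is 0.948 x 2 = 1.90 ml/s.

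**Step 2: precision of the planned Part A model.** Residual df = 30 - 10 - 2 - 2 = 16. Half-width = t(0.975, 16) x SDw x sqrt(2/10) = 2.120 x 0.447 SDw = 0.948 SDw.

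**Step 3: precision with a visit-level volume term.** Residual df = 15. Half-width = 2.131 x SDw x sqrt(0.2 x (1 - rho^2) x (1 + 1/14)), where the last factor allows for estimating the slope. At rho = 0 this is 0.987 SDw, a ratio of 0.987/0.948 = 1.041. For other values, multiply 1.041 by sqrt(1 - rho^2).

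| Assumed rho | Ratio by formula | Ratio in 6000 simulated trials |
|---|---|---|
| 0 | 1.04 | 1.038 |
| 0.3 | 0.99 | 0.990 |
| 0.5 | 0.90 | 0.899 |
| 0.7 | 0.74 | 0.742 |

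Break-even: 1 - rho^2 = 1/1.041^2 = 0.923, so rho is about 0.28 (about 0.27 in simulation). At rho 0.5 the adjusted interval is narrower in 77% of trials, so in 23% it is not. For Part B, assuming 10 subjects x 2 visits, df falls from 8 to 7. The ratios are 1.10, 1.05, 0.95 and 0.78 at the same four values, with break-even at about 0.40.

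**Step 4: bias.** With randomised order, a difference in volume between products is chance, and the planned interval already allows for it. The adjusted model is more exposed, because its covariate is measured during or after the procedure. Suppose urine lost outside the catheter lowers one product's volume sum by d within-subject SDs of volume and leaves recorded flow unchanged. The adjusted contrast is then off by about rho x d:

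- d = 0.5, rho = 0.5: 0.25 SDw (simulated 0.24), coverage 92%.
- d = 1, rho = 0.5: 0.50 SDw (simulated 0.50), coverage 82%.

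The planned model keeps 95% coverage in both. If the loss also lowers recorded flow, the picture can reverse: with volume down 0.5 SD and flow down 0.25 SD, the planned contrast is off by about 0.23 SDw (coverage 92%) and the adjusted one is near zero. The documents cannot say which scenario applies.

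**Step 5: could a check on the covariate make adjustment safe?** One could discard the adjusted result when the volume sum differs by product. The SE of a product difference in mean volume is sqrt(2/10) = 0.447 SD. A 5% test on 16 df therefore has noncentrality 0.5/0.447 = 1.12 for a 0.5 SD shift (power 18%) and 1/0.447 = 2.24 for a 1 SD shift (power 56%). Among trials that pass the test despite a 1 SD shift, adjusted coverage is 79%, no better than the 82% without any check. A fixed 0.5 SD threshold would be crossed by some pair of products in about half of trials by chance alone.

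**The case for a change.** The best case for adjustment is this. The readable text gives no filling rule, and subjects pass urine for a sample just before catheterisation, so volume probably does vary. In a trial without success criteria, estimates and intervals are the main product. In simulation, adjustment moved a contrast by a mean of 0.17, 0.23 and 0.30 SDw when volume explained 20%, 40% and 60% of within-subject flow variance. The difference detectable with 80% power fell from 1.33 SDw to 1.24, 1.07 and 0.88. A choice that can move estimates this much is better made in advance. Using the sum rather than drained volume alone also helps: urine left behind by one catheter moves from one component to the other and cancels.

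Much of this stands. Age is the only named covariate, both volumes are available, and a pre-specified adjustment would carry more weight than a post-hoc one. But the gain depends wholly on an assumed correlation, and the redacted test-visit text may already standardise filling, which would leave little to adjust for. The cancellation holds only if no urine escapes measurement and the hand-held scan is accurate. One component is also a secondary endpoint that section 5.2 hypothesises the new catheters will reduce. These are reasons why a statistician might add the analysis, not evidence that the plan is wrong without it.

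**Conclusion.** The concern does not hold. Age is a redundant covariate with complete data and has a small effect when visits are missing; neither is an error. Omitting volume leaves the randomised comparison free of systematic bias, and no rule or figure in section 7.1 is shown to be wrong. What remains is an optional supportive analysis. Its effect on the Part A interval runs from 4% wider to 26% narrower across assumed correlations of 0 to 0.7, and it adds a risk of bias that a check on ten subjects cannot reliably detect. Section 7.1 already lets the volumes be summarised and explored.

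This rests on the readable Part A layout, randomised order, and errors in the volume measurement being possible but of unknown direction. It would need another look if the trial were confirmatory, or if the documents showed a strong within-subject link between volume and flow together with a volume measured before catheterisation.

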7.2. Sample size

As this is an exploratory study no formal sample size calculation has been performed. It is assumed that 10 subjects will be adequate for obtaining indications on performance and acceptance.

7.3. Level of significance and power

Statistical tests will be carried out as two sided tests on a 5% level of significance.

7.4. Drop-out

NA

7.5. Pass/fail criteria

No formal success criteria are applied in this explorative investigation. The investigation will provide valuable insight into both performance and acceptance of three new intermittent catheters

7.6. Interim analysis

There is no planned interim analysis in this investigation.

7.7. Statistical reason for termination of investigation

There will be no interim analysis and therefore no reason to terminate the investigation based on statistical considerations.

7.8. Deviation(s) from statistical plan

Any deviations from the statistical plan will be documented in the clinical investigation report.

8. Data management

8.1. Data review, database cleaning, and issuing and resolving data queries

Data management and statistical analyses is carried out by Medical Affairs, Coloplast A/S.

To ensure correct data entry, data is entered twice (double data entry). Data management is responsible for control of data consistency and for completeness of data from each subject.

Discrepancies are listed in Data Query Forms (DQF), and the Investigator is responsible for solving these promptly. When all DQFs are solved the database is locked and the statistical analyses are performed.

8.2. Verification, validation and securing of electronic clinical data systems

EXPeRT Data Management, version 5.0.05 system delivered by OmniComm Systems Inc. is used for data management. The system is designed to be compliant with the requirements of 21 CFR part 11. It is a validated data management system allowing only qualified and trained personnel to enter the system.

